1.1 Synopsis

This study investigates the effectiveness of Virtual Reality (VR)-assisted rehabilitation on improving shoulder joint range of motion (ROM) and reducing pain in female collegiate basketball players with shoulder impairments. The study will compare the effects of VR-assisted rehabilitation, traditional rehabilitation, and a control group (no intervention) over a 9-week period.

1.2 Study Design and Overview

This is a randomized controlled trial (RCT) with three groups:

- VR-Assisted Rehabilitation Group: Participants will engage in immersive, shoulder-specific rehabilitation using VR technology.
- Traditional Rehabilitation Group: Participants will undergo standard shoulder rehabilitation exercises (e.g., mobility drills, resistance band exercises).
- Control Group: Participants will not receive any rehabilitation intervention but will continue with their regular basketball training.

1.3 Schedule of Activities

Pre-Study Screening: July 15, 2024: Initial screening to assess eligibility (e.g., shoulder impairments, regular participation in basketball).

Intervention Period: July 15 to September 13, 2024: Participants will undergo their respective rehabilitation protocols (VR-assisted, traditional, or control).

Final Assessment: September 13, 2024: Post-intervention evaluations of shoulder ROM and pain levels.

2. Introduction

2.1 Study Rationale

Shoulder injuries are common in sports, particularly in basketball, and can significantly impact athletic performance and recovery. Traditional rehabilitation methods often lack engagement and personalized feedback, potentially hindering recovery. Virtual Reality (VR) offers a unique, immersive environment for rehabilitation, potentially improving adherence, engagement, and outcomes. This study aims to assess whether VR-assisted rehabilitation can offer superior results in improving shoulder ROM and reducing pain compared to traditional methods.

2.2 Background

Previous studies have demonstrated the potential of VR for musculoskeletal rehabilitation, including its ability to simulate functional movements, provide real-time feedback, and increase patient engagement. However, there is limited research on VR's use specifically for shoulder rehabilitation in active, young athletes, particularly female basketball players. This

gap in the literature presents an opportunity to explore the effectiveness of VR in improving athletic rehabilitation outcomes.

2.3 Risk/Benefit Assessment

Known Risks: Potential discomfort or fatigue from physical activity or VR simulation fatigue. However, these risks will be minimized through careful monitoring and adjusting the intensity of the exercises.

Known Benefits: Improved shoulder ROM, reduced pain, and increased rehabilitation engagement. These benefits are crucial for accelerating recovery and ensuring athletes can return to their sport as soon as safely possible.

Ethical Oversight: The study has been approved by the Ethics Review Committee of Sanming Medical and Polytechnic Vocational College, and all participants will provide informed consent.

3. Objectives and Endpoints

3.1 Primary Objectives

To assess the effectiveness of VR-assisted rehabilitation in improving shoulder ROM in female collegiate athletes with shoulder impairments.

3.2 Secondary Objectives

To compare the impact of VR rehabilitation and traditional rehabilitation on pain levels (measured using the Visual Analog Scale (VAS)).

To evaluate participant engagement and adherence to rehabilitation protocols in both VR and traditional rehabilitation groups.

4. Study Design

4.1 Overall Design

This study will be a randomized controlled trial (RCT) with three groups: VR-assisted rehabilitation, traditional rehabilitation, and a control group. Participants will be randomly assigned to one of the three groups. Pre- and post-intervention measurements of shoulder ROM and pain levels will be collected.

4.2 Scientific Rationale for Study Design

The randomized controlled design minimizes bias and allows for clear comparisons between the groups. By using a control group, we can assess whether the VR intervention leads to improvements beyond the natural progression of rehabilitation or training.

4.3 Justification for Intervention

Given the potential of VR to engage participants and provide interactive, task-specific rehabilitation, it is hypothesized that VR-assisted rehabilitation will lead to greater improvements in shoulder ROM and pain reduction compared to traditional methods.

4.4 End-of-Study Definition

The study will conclude on September 13, 2024, after all post-intervention assessments are completed.

5. Study Population

5.1 Inclusion Criteria

- Age Requirement: Female Chinese college basketball players aged between 18 and 24.
- Shoulder Injury Requirement: Diagnosed with shoulder joint injuries (e.g., rotator cuff injuries, tendon damage, shoulder dislocation) with no previous surgical treatment.
- Sports Background: Participating in basketball training with at least three training sessions per week and a certain level of sports experience.
- Informed Consent: Willing to participate in the study and sign the informed consent form, with the ability to understand and cooperate with the research-related questionnaires and treatment plans.
- Physical Health: No severe cardiovascular, neurological, or musculoskeletal disorders that impact physical performance.

5.2 Exclusion criteria

1. Disease Exclusion: Individuals with a history of severe shoulder surgeries or other types of shoulder injuries (e.g., fractures, severe shoulder joint diseases).
- Medication Use: Those who are using any medication that may interfere with shoulder rehabilitation (e.g., steroids, painkillers, etc.) during the trial.
- Mental Health Issues: Individuals with severe psychiatric conditions, such as depression, anxiety, etc., who are unable to independently complete virtual reality rehabilitation treatment.
- Other Contraindications: Individuals who have adverse reactions to virtual reality technology, such as those with severe motion sickness.

5.3 Study Interventions

- VR-Assisted Rehabilitation Group: Participants will engage in immersive VR rehabilitation using the PICO 3 Pro system.
- Traditional Rehabilitation Group: Participants will undergo conventional rehabilitation exercises, such as resistance training and mobility drills.

- Control Group: Participants will not receive any formal rehabilitation intervention but will continue with their usual basketball training.

5.3 Recruitment and Retention

Participants will be recruited from three universities in Fujian Province. Retention will be ensured through regular follow-ups, clear communication about the study's purpose, and offering incentives for participation.

6. Study Interventions

6.1 VR-Assisted Rehabilitation Group

Participants will engage in immersive VR rehabilitation using the PICO 3 Pro system. This system includes motion tracking and interactive rehabilitation tasks that mimic basketball-related movements, progressively increasing in difficulty.

6.2 Traditional Rehabilitation Group

Participants will undergo conventional rehabilitation exercises, such as resistance training and mobility drills, guided by a physical therapist.

6.3 Control Group

Participants will not receive any formal rehabilitation intervention but will continue with their usual basketball training.

7. Discontinuation and Withdrawal

7.1 Discontinuation of Intervention

If a participant experiences excessive discomfort or injury during the rehabilitation process, they will be allowed to withdraw from the study. The study protocol allows for flexible adjustments to ensure participants' safety.

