7.2 Participant Withdrawal

Participants may withdraw from the study at any time without penalty. Withdrawal reasons will be documented to ensure data integrity.

8. Study Assessments

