10.3 Participant Protection

The study ensures participant protection through:

Minimizing Risk: Interventions are non-invasive, with regular monitoring for any adverse effects.

Confidentiality: All data will be anonymized and securely stored.

Ethical Oversight: The study adheres to the Declaration of Helsinki and national ethical guidelines.

11. Participant Timeline

Stage	Timeline	Description
Recruitment	July 15 • July 18, 2024	Participants are recruited, screened, and provided with the informed consent form.
Screening and Baseline Assessment	July 19 • July 21, 2024	Initial assessments of shoulder ROM and pain levels (VAS), confirmation of eligibility.
Pre-Intervention Evaluation	July 22, 2024	Final baseline evaluation and randomization of participants into intervention groups.
Intervention Period	July 22 • September 9, 2024	Participants undergo 9 weeks of VR-assisted or traditional rehabilitation, or no intervention (control group).
Mid-Point Evaluation	August 15, 2024	Mid-intervention check-in to assess progress, adherence, and potential adjustments.
Post-Intervention Evaluation	September 10 • September 13, 2024	Final assessments of shoulder ROM and pain levels, along with participant feedback on engagement.
Follow-Up	September 13, 2024	Final data collection and study conclusion.

12. Data Management Plan

All participant data, including demographic information, assessment results (range of motion and pain scores), and session attendance, will be collected and recorded on standardized data collection forms. Each participant will be assigned a unique study ID number to ensure confidentiality.

Data Handling Procedures:

- Paper-based data will be digitized and stored in a password-protected, encrypted database on a secure personal computer accessible only to the research team.
- Electronic data will be backed up weekly on an encrypted external hard drive.
- All personal identifiers will be removed from the dataset before analysis.
- Only de-identified data will be shared in publications or public databases.

Data Integrity and Quality Control:

- Double data entry will be employed to reduce transcription errors.
- Data will be periodically reviewed for completeness and consistency.
- Any missing data will be handled using appropriate statistical imputation methods or sensitivity analyses, as described in the statistical plan.

All procedures will comply with ethical guidelines for the protection of human participants and data privacy.

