13. Safety Monitoring

Although the interventions in this study are non-invasive and carry minimal risk, appropriate safety monitoring procedures will be implemented to ensure participant well-being.

Key Safety Procedures:

- All participants will be screened before enrollment to ensure eligibility and minimize risk.
- A licensed physical therapist will supervise each VR rehabilitation session to monitor physical exertion and movement quality.

- Participants will be instructed to report any signs of discomfort, dizziness, pain, or fatigue immediately during or after each session.

Adverse Event Handling:

- Any adverse events (AEs), whether mild or serious, will be documented and evaluated by the investigator.
- Participants experiencing significant AEs will be referred for medical evaluation and may be withdrawn from the study if necessary.
- A safety log will be maintained for transparency and accountability.

Regular check-ins and post-session debriefings will be conducted to ensure both physical and psychological safety throughout the study.

14. Limitations of the Study

While this study is designed with scientific rigor and careful planning, several limitations must be acknowledged:

1. Sample Size: The relatively small sample size ($n = 40$) may limit the statistical power and generalizability of the results to larger populations or different athletic groups.
2. Short Intervention Duration: The 4-week intervention period, although adequate for observing changes in ROM and pain, may not capture long-term rehabilitation outcomes or recurrence rates.
3. Single-Center Study: Conducting the study at a single university or region may introduce selection bias and limit external validity.
4. Self-Reported Pain Measures: The use of self-reported Visual Analogue Scale (VAS) scores for pain may be influenced by individual perceptions and psychological factors.
5. Participant Adherence: Although engagement is expected to be high in VR-assisted groups, individual differences in motivation, fatigue, or scheduling conflicts may affect adherence to the protocol.

Future studies with larger sample sizes, multicenter designs, longer follow-up periods, and objective pain assessments (e.g., biomarkers, neuroimaging) are recommended to validate and extend the findings.

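### Stopping the intervention is not separated from leaving the study, and nothing says that participants who stop still have final ROM and VAS measured

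*Protocol*

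**What the plan says.** Three places in the protocol deal with exit:

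- **Section 7.1 (Discontinuation of Intervention):** "If a participant experiences excessive discomfort or injury during the rehabilitation process, they will be allowed to withdraw from the study". Its only other sentence allows unspecified flexible adjustments for safety.
- **Section 7.2 (Participant Withdrawal):** anyone may leave at any time. The only follow-through is that "Withdrawal reasons will be documented to ensure data integrity".
- **Section 13 (Safety Monitoring):** "Participants experiencing significant AEs will be referred for medical evaluation and may be withdrawn from the study if necessary".

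The measurement plan is short. Section 4.1 states: "Pre- and post-intervention measurements of shoulder ROM and pain levels will be collected". In the section 11 timeline, the September 10–13 row reads "Final assessments of shoulder ROM and pain levels, along with participant feedback on engagement". The August 15 row reads "Mid-intervention check-in to assess progress, adherence, and potential adjustments", which names neither ROM nor VAS.

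Section 12 says of gaps in the data: "Any missing data will be handled using appropriate statistical imputation methods or sensitivity analyses, as described in the statistical plan". The section on recruitment and retention offers regular follow-ups, clear communication and incentives. It does not mention people who have stopped the intervention.

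**The concern.** Stopping a treatment and leaving a trial are different events. A person can do the first and still be measured. Here the heading announces the first and the text provides only the second. A site that follows the text could let a participant with a sore or re-injured shoulder leave, record why, and never obtain a final value.

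The named triggers are not neutral. Shoulder ROM is the primary outcome (section 8.1) and VAS pain a secondary one (section 8.2). Discomfort and injury bear directly on pain and plausibly on ROM, so the values lost would tend to come from people doing badly. There is one scheduled ROM/VAS assessment after baseline, so a participant who leaves before it would normally contribute baseline values alone.

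The amount of loss could differ by arm. The trigger in 7.1 arises during rehabilitation, which points mainly to the two active arms. Sections 7.2 and 13 cover everyone, and for the control arm section 6.3 says "Participants will not receive any formal rehabilitation intervention but will continue with their usual basketball training". Those are injured players who keep training, so loss there is also possible.

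**Working it through.** **Text check.**

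| Question | Where | Answer |
|---|---|---|
| Which exit is named for discomfort or injury? | 7.1 | From the study; optional |
| Is there a status of stopped but still assessed? | 7.1, 7.2, 13 | None described; flexible adjustment is not an exit |
| Which exit is named for significant AEs? | 13 | From the study; optional |
| What is kept when someone withdraws? | 7.2 | The reason |
| When are ROM and VAS measured? | 4.1, 11 | Before, and September 10–13 |
| Is the final assessment extended to those who stop? | 11, retention section, 12 | Not stated; not barred either |

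**Illustration of size.** The protocol gives no dropout rate and no estimate of bias, so there is no figure of its own to reproduce. The one input from the document is 15 per group (section 9.2). Assumed: normally distributed change scores with SD 1, no true effect, a two-sided 5% level, completers only, 3 of 15 lost in one arm and none elsewhere, and correlation ρ = 0.3, 0.5 or 1.0 between the reason for loss and the outcome.

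*Mean shift when exactly the three worst-placed of 15 are lost.* The expected values of the three lowest normal order statistics for n = 15 are −1.736, −1.248 and −0.948, with sum −3.932.

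Shift = ρ × 3.932 / (15 − 3) = ρ × 0.328

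- ρ = 0.3: 0.098 SD
- ρ = 0.5: 0.164 SD
- ρ = 1.0: 0.328 SD

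*Mean shift when each person is lost on their own value, with probability 3/15 = 0.2.* The cut-off is z = −0.842 and the normal density there is 0.280.

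Shift = ρ × 0.280 / 0.8 = ρ × 0.350, that is 0.105 / 0.175 / 0.350 SD. The two versions agree closely.

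*Type I error.* This used 200,000 simulated null trials per scenario, with three arms of 15 and each person lost on their own value. The test was a one-way F-test on change in completers, which equals the group-by-time test of a pre/post repeated-measures ANOVA (section 9.3).

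| Expected losses per arm | ρ = 0.3 | ρ = 0.5 | ρ = 1.0 |
|---|---|---|---|
| 3 in one arm only | 0.057 | 0.068 | 0.13 |
| 3 in every arm | 0.050 | 0.050 | 0.049 |

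The second row behaves as theory says. If the same mechanism acts in every arm, completers in all arms are independent draws from one distribution, so the test keeps its level. If the one arm with loss is control, the size is the same and the direction reverses.

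**The case against.** The strongest reply is that the text is silent rather than wrong. Every exit is optional, the right to withdraw is standard, and nothing closes the September assessment to a person who has stopped. A reader might infer that 7.1 obliges people who stop to leave, or that the final visit is for completers only. The documents support neither reading. Similarly, the August check-in is meant to assess progress. An interim ROM or VAS value is unlikely given section 4.1, but it is not excluded.

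A second reply is that the retention measures are not limited to people still on treatment, and that section 12 plans imputation or sensitivity analyses under a statistical plan not shown here. The illustration assumes completers only, which is not what section 12 describes. That is a fair limit on the numbers. Imputation could draw on baseline values, attendance, reasons for withdrawal and the safety log.

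A third is that bias needs clearly unequal loss together with a fair correlation, and the protocol implies neither. A reader might also infer that any pain-related dropout inflates the type I error. It does not when loss is similar across arms.

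What remains is this. Whether someone who stops is still measured is a rule of trial conduct. Section 7.1 addresses that event and merges it with study exit. No analysis plan can replace an outcome that was never collected, and imputation would have no observed final values from people who stopped to check itself against.

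**Conclusion.** The point holds as a weakness of wording with a real but uncertain consequence. The protocol permits, without requiring, the loss of final ROM and VAS for reasons linked to those outcomes.

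The harm depends on how unequal the loss is. If one arm alone lost about a fifth of its participants, the effect would be small at a correlation of 0.3, moderate at 0.5, and substantial only in the worst case of 1.0. These figures rest on assumed loss rates and correlations and on a completers-only analysis. The documents do not allow the actual size or direction of any bias to be derived, and it should not be claimed that the result would favour a particular arm. The case for change rests on the text and on values that cannot be recovered later, not on a predicted bias.

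**What to change.** In sections 7.1, 7.2 and 13, separate stopping the assigned intervention from leaving the study. State that every randomised participant who stops, in any arm, is invited to the September 10–13 ROM and VAS assessment unless she withdraws consent. It would help to repeat this in the retention section.

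The cost is a few sentences and a few extra visits within a window already planned. The right to withdraw is untouched. When treatment is stopped remains a matter for the sponsor and the investigator.

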7.2 Participant Withdrawal

Participants may withdraw from the study at any time without penalty. Withdrawal reasons will be documented to ensure data integrity.

8. Study Assessments

8.1 Primary Outcome

Shoulder ROM: Measured using a digital goniometer to assess shoulder flexion, abduction, extension, internal rotation, and external rotation.

8.2 Secondary Outcome

Pain Intensity: Measured using the Visual Analog Scale (VAS), a 10 cm horizontal line indicating pain intensity from 0 (no pain) to 10 (worst imaginable pain).

Participant Engagement: Measured through self-report surveys assessing adherence to rehabilitation protocols and the perceived effectiveness and satisfaction with the intervention.

9. Statistical Considerations

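### Adherence is a secondary objective, but its only defined outcome measure is a self-report survey, while the session attendance that the trial records is assigned to no outcome

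*Protocol*

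**What the plan says.** - **Objective (Protocol 3.2).** The second secondary objective is "To evaluate participant engagement and adherence to rehabilitation protocols in both VR and traditional rehabilitation groups".
- **Outcome (Protocol 8.2).** Under the label Participant Engagement, the measure is "Measured through self-report surveys assessing adherence to rehabilitation protocols"; the sentence goes on to add perceived effectiveness and satisfaction. No other outcome definition mentions adherence.
- **Data collected (Protocol Section 12).** Among the items listed, "session attendance, will be collected and recorded on standardized data collection forms". Sections 3, 8 and 9 do not refer to attendance.
- **Timeline (Protocol Section 11).** The evaluation on August 15, 2024 is described as "Mid-intervention check-in to assess progress, adherence, and potential adjustments". No method is given, and the check-in is not named as an outcome.
- **Supervision.** In the VR arm, "A licensed physical therapist will supervise each VR rehabilitation session" (Section 13). In the traditional arm, the exercises are "guided by a physical therapist" (6.2).
- **Expectation.** Section 2.1 gives better adherence and engagement as a possible advantage of VR. Section 14 expects high engagement in the VR arm.

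**The concern.** Adherence is something participants do; satisfaction and perceived effectiveness are what they think of it. Section 8.2 obtains both from participants' own answers, under one outcome label. The arms cannot be masked, since a participant knows whether she is wearing a headset. Novelty or expectation could therefore raise reported adherence in the VR arm even if both arms attend equally.

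Section 14 accepts this kind of weakness for pain, where it lists self-reported VAS scores as a limitation. It does not extend that caution to adherence, although for adherence the trial holds a less subjective record. At stake is one secondary conclusion, that VR improves adherence, which belongs to the trial's rationale in 2.1.

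**Working it through.** **1. Measure against data, section by section**

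| Place in Protocol | What it fixes about adherence |
|---|---|
| 3.2 | An objective, for the VR and traditional arms |
| 8.2 | The only outcome definition: self-report surveys |
| 9.1, 9.3 | No adherence hypothesis and no adherence test |
| 11 | Adherence looked at mid-way; no method, no outcome status |
| 12 | Session attendance collected; not linked to any outcome |

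The protocol therefore names the more bias-prone of two available sources and leaves the other unassigned.

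**2. How far differential reporting could matter (illustration only)**

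The protocol states no figure for adherence, so there is none to reproduce. Input from the document: 15 per group (9.2). Assumptions: a percentage scale, no true difference, a two-sided 5% t-test of VR against traditional, SD of reported adherence 15 to 25 points, and VR over-reporting by 5 or 10 points more than traditional.

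- Standard error = SD × √(2/15): 5.48, 7.30 and 9.13 points for SD 15, 20 and 25.
- Noncentrality = bias / standard error. Degrees of freedom = 15 + 15 − 2 = 28; critical value 2.048.
- Rejection rate = P(|T| > 2.048), with T noncentral t.

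| Assumed bias | SD 15 | SD 20 | SD 25 |
|---|---|---|---|
| 5 points | 14% | 10% | 8% |
| 10 points | 42% | 26% | 18% |

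For example, 10 points at SD 20 gives 10 / 7.30 = 1.37 and a rejection rate of 26%.

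The same check in SD units needs no scale. With a normal approximation, the rejection rate is Φ(b/√(2/15) − 1.96) + Φ(−b/√(2/15) − 1.96). It gives 5%, 10.5%, 27.8%, 53.7% and 78.2% for b = 0, 0.25, 0.5, 0.75 and 1.0 SD. The value at 0.5 SD agrees with the t-test's 26%, allowing for the approximation.

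**3. Can an attendance proportion be formed from the protocol as written?**

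Not yet. No section states a number or frequency of rehabilitation sessions, and the durations conflict:

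- 9 weeks in 1.1 and in the Section 11 description.
- July 22 to September 9 in the same row of Section 11: 9 days to July 31, 31 in August and 9 in September make 49 days, or 7 weeks.
- 4 weeks in Section 14.

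The numerator is collected, but the denominator is undefined.

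**The case against.** Several points can fairly be made in the protocol's favour.

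- **Adherence is not looked at by survey alone.** Attendance is recorded and the mid-point check-in considers adherence. This stands as a limit on the point: the survey is the only *defined outcome measure*, not the only source of information. An unseen SAP might bring attendance in. But 8.2 already names a measure, so this is a choice the protocol makes and not a detail it leaves open.
- **A reader might infer that adherence, satisfaction and perceived effectiveness form one instrument or one pooled score.** The text does not support that. It speaks of surveys in the plural and describes no scoring. What it shows is that all three are self-reported under one outcome label.
- **A reader might infer a planned between-arm test of adherence.** None is specified. Section 3.2 sets out to compare pain but to evaluate adherence in both groups, 9.1 covers ROM and pain only, and 9.3 contains no adherence test. A contrast between the arms is a natural reading given 2.1, but it is not the protocol's wording.
- **The rejection rates rest on assumed bias and SD.** This stands. They show what a biased measure would do, not that the bias exists or how large it is.
- **Attendance is imperfect too.** This also stands. It misses effort and completion within a session. Supervision of every session is stated only for the VR arm, and the protocol does not say who records attendance or whether any traditional exercise is done unsupervised.

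**Conclusion.** The point holds in a limited form. The protocol makes adherence an objective, defines its outcome measure as self-report from unmasked participants, and assigns the attendance it records to no outcome. If the arms are contrasted on the survey, differential reporting could pass for a VR benefit. Under the assumptions above, the false-positive rate would be 8% to 42% instead of 5%. Those figures are illustrative, because the documents give no survey scale, SD or adherence test.

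A reader might go further and conclude that the trial is set to report a false adherence benefit. The documents do not support that: they show neither a reporting bias nor a planned test. Priority is low to moderate, since part of one secondary objective is affected and the ROM and pain analyses are not.

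**What to change.** 1. In 8.2, name attendance from the Section 12 record as the main adherence measure: sessions attended out of sessions scheduled, recorded in the same way in the VR and traditional arms.
2. Report the survey items separately, labelled as self-reported engagement, satisfaction and perceived effectiveness. Keep self-reported adherence as a supporting measure.
3. State the number of scheduled sessions in each of the two arms, and reconcile the durations in 1.1, 11 and 14. Without this the proportion has no denominator.
4. State whether the mid-point check-in contributes to the adherence outcome and, if so, how.

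**Cost.** No new type of data is needed, because attendance is already on the forms. The change is more than an edit to 8.2: the schedule must be stated, the durations reconciled, and attendance recording aligned between the arms. The downside is that attendance does not capture effort or exercise completion within a session, which is why the survey stays.
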